1.4.3 Histone Acetylation, HDAC Inhibitors and Direct Effects in Melanoma Cells

As expected, HDAC inhibitors (HDACi) modulate expression of thousands of genes in melanoma. More specifically, HDACi inhibit expression of anti-apoptotic proteins survivin, bcl-XL, bcl-2, Mcl-1, XIAP, reduce expression of cFLIP, an inhibitor of TNF-related apoptosis, and induce expression of pro-apoptotic proteins BIM, BAX, BAK, and CDKN1A⁶⁸. Equally important, class I HDACi may alter immunogenicity by upregulating expression of melanoma differentiation antigens, class I and class II MHC antigens, antigen processing and presenting machinery (TAP1, TAP2, LMP2, LMP7, tapasin, CIIA), costimulatory molecules (CD40, CD86), ligands of activating receptor on NK cells (MICA, MICB), and PD-L1/PD-L2 genes *in vitro*⁶⁹⁻⁷². **The ultimate effect of HDAC inhibition in melanoma can be suppression of cell proliferation, increased immunogenicity, and increased apoptosis.**

1.4.4 Histone Acetylation, HDAC Inhibitors and Effects on Host Immune Response

It is important to emphasize that DNA methylation and histone modifications regulate development, differentiation, activation, and memory lineage function of host immune response⁷³. In particular, selective demethylation of several specific CpG dinucleotides in the promoter region of IFN-γ, IL-3 and IL-13 genes regulate T helper cell differentiation into Th1, Th2, Th17 and induction of regulatory T cells. Signaling through cytokines activates transcription factors (STAT4, STAT6, GATA-4, T-bet), which facilitates chromatin remodeling (long-range H4 acetylation, H3K9 trimethylation) at the enhancer regions of T helper cell-specific genes and ultimately influences activation and T cell differentiation (reviewed in⁷⁴).

Not surprisingly, HDACi have pleiotropic effects on immune cells. Therefore, the net effect remains ill-defined as HDACi can also impair immune surveillance and induce hematologic toxicity in cancer patients depending on the dose, type and selectivity of HDACi used. For example, panobinostat can have differential effects on T cell viability and function, depending on the dose used^{75,76}. Similar dose-dependent results were seen with entinostat⁷⁷. Nevertheless, several positive effects of HDACi were seen, such as the activation and inhibition of apoptosis of CD4+ cells⁷⁸, CD8+ cells⁷⁹, macrophages⁸⁰, T regulatory cells⁸¹, and myeloid-derived suppressor cells (MDSC)⁸².

1.4.5 Preclinical Evidence about the Role of Histone Deacetylation Inhibition in Melanoma

Treatment with a pan-HDACi (LBH589) enhanced survival and proliferation of tumor antigen-specific T cells and suppressed the T regulatory (Treg) population when coadministered with gp100-specific T cells in a B16 melanoma model⁷⁹. The pan-HDACi lost its antitumor effect in immunodeficient as opposed to immunocompetent mice⁷⁰. Concurrent LBH589 (15mg/kg, M-W-F) and PD-1 blockade (3mg/kg, Tu-Th) in C57BL/6 mice showed delayed growth and enhanced survival of B16-F10-bearing melanoma tumors⁶⁹, similar to results seen in a lung adenocarcinoma model⁸³. Entinostat has effects in MDSC^{82,84}, Treg⁸¹, and dendritic cells⁸⁵. When administered as a single-agent orally no antitumor responses were seen in patients with metastatic melanoma⁸⁶.

1.4.6 Entinostat

1.4.6.1 Non-Clinical studies

Entinostat (pyridine-3-yl)methyl((4-[(2-aminophenyl)carbamoyl]phenyl)methyl) carbamate), or SNDX-275, MS-275 is an orally available inhibitor of HDACs 1, 2, 3, and 11 [IC₅₀ (nM) 124, 139, 187, 427, respectively]. The selectivity of entinostat for these HDAC isoforms may account for its better safety and efficacy compared to other nonselective pan-HDAC inhibitors^{87,88}. Exposure of various cancer cell lines to entinostat resulted in accumulation of hyperacetylated histones at concentration between 0.3-1 μM and gene expression changes in various cell processes, such as cell growth, apoptosis, differentiation, cell communication, regulation of transcription, cell signaling, and chromosome organization. Entinostat demonstrated broad, dose-dependent, tumor-inhibitory effects against cancer cell lines with IC₅₀ values ranging between 0.04-4.71 μM. Entinostat showed tumor growth inhibition in human tumor xenografts from diverse cancer types, such as melanoma, non-small cell lung cancer, and breast cancer. The maximum tolerated dose in the animal experiments was 50mg/kg daily.

As predicted by its epigenetic mechanism of action, entinostat may restore sensitivity in resistant cancer cell lines *in vitro* and *in vivo* when combined with various classes of anticancer agents, such as chemotherapies, anti-estrogens, EGFR inhibitors, DNA methyltransferase (DNMT) inhibitors and immunotherapies.

Examples of entinostat in combination with hormonal therapies (aromatase inhibitor, selective estrogen modulators) and DNA methylase transferase inhibitors ('dual epigenetic blockade') are provided in the Investigators' Brochure and elsewhere^{89,90}.

Proof-of-principle experiments in syngeneic murine models that bear poor or modestly immunogenic tumors suggest that resistance to concurrent CTLA-4 and PD-1 blockade can be restored with entinostat. In these models primary targets of entinostat were actually circulating granulocytic MDSC, which are known to be immunosuppressive, whereas the function of CD8+ cells remained intact⁸². In other preclinical models entinostat reduced transcription of FoxP3 in circulating Treg, an important transcription factor for survival and function of this other immunosuppressive population⁸¹. In other clinical models entinostat can induce favorable changes in effector T cell response against cancer cells⁹¹. The entinostat-induced reduction of circulating MDSC was confirmed in a clinical study of entinostat in combination with aromasin compared with aromasin alone⁸⁴. Reduction of circulating Tregs and monocytic MDSC was also seen in a clinical trial of entinostat administered in combination with high dose bolus IL-2 in patients with advanced renal cell carcinoma⁹². Entinostat also showed single-agent activity against xenograft melanoma models⁹³ and in combination with temozolomide⁶⁵ and interleukin-2⁹⁴.

Entinostat administered in rats at doses comparable to those currently used in clinical studies had no effects in various physiologic systems (cardiovascular, central nervous, respiratory, GI, and urogenital), with the exception of diuresis and increased excretion of Na⁺, K⁺, Cl⁻, and creatinine.

Pharmacokinetic studies of entinostat administered across various animal models show considerable differences with respect to oral bioavailability, serum half-life ($t_{1/2}$), area-under-curve (AUC) exposure, peak serum concentrations (C_{max}), time-to-peak serum concentrations (t_{max}). Food decreased absorption of entinostat. The highest serum concentrations were seen in liver, kidney, spleen, and glandular tissue. Entinostat was moderately stable in preparation of human hepatocytes and liver microsomes. Reversible inhibition by entinostat was demonstrated for CYP2C8 and CYP3A4 and glycuronidation was the major method of metabolism. Entinostat is excreted equally by urine and biliary tract.

Toxicologic studies of entinostat across various animals suggested effects on the skin, atrophy of lymphatic organs, myelosuppression, GI toxicity, loss of appetite, weight loss, changes in renal function, hypercholesterolemia, reduced fertility, and teratogenicity.

1.4.6.2 Effects of Entinostat in Humans

As of September 29 2016, Entinostat has been administered in >1,000 cancer patients across pharma-sponsored studies (Syndax, Syndax predecessors, NCI, Kyowa Hakko Kirin Co., Ltd -the company that bears development and commercialization rights of entinostat in Japan and Korea). This number does not

include patients who were treated as part of investigator-initiated studies. In particular, clinical studies investigated entinostat as monotherapy [6 studies had reportable data at the time; 4 studies in patients with solid tumors (n=128), and 2 studies in patients with hematologic malignancies (n=89)] and in combination with other systemic treatments [22 studies had reportable data at the time; 17 studies in patients with solid tumors (n=535) and 5 in patients with hematologic malignancies (n=205)].

1.4.6.2.1 Pharmacokinetic Studies

Pharmacokinetic data, which were compiled from 4 studies, showed linear dose-dependent pharmacokinetics based on single and repeated dose administrations. Entinostat absorption is facilitated by low pH in the stomach and its metabolism is mediated by UGT 1A4, but not by CYP enzymes. Entinostat mean terminal $t_{1/2}$ was approximately 194 hours based on the radiolabeled absorption, distribution, metabolism, and excretion (ADME) study with the majority of the radioactive dose excreted in urine (71%) and feces (12%). Entinostat and/or its metabolites partition preferentially into erythrocytes, with greater affinity to binding sites on erythrocytes relative to those in plasma. In fact, the slow dissociation rate of entinostat from erythrocytes may account for the long $t_{1/2}$ of entinostat.

1.4.6.2.2 Safety in Human Clinical Studies

An integrated analysis across all industry-sponsored and NCI-sponsored studies with available safety data showed that single-agent entinostat was well tolerated at the doses and schedules investigated. The most frequent adverse effects (AE), predominantly grade 1-2, included fatigue, nausea, vomiting, anorexia, diarrhea, hematologic abnormalities (anemia, thrombocytopenia, neutropenia, leukopenia), and metabolic abnormalities (hypoalbuminemia, hypophosphatemia, hyperglycemia, and hyponatremia). Certain types of AEs were more frequent in patients with solid tumors than in those with hematologic malignancies; for example, hypoalbuminemia (59%), fatigue (58%), nausea (57%), hypophosphatemia (45%), anemia (42%), and thrombocytopenia (41%) were more frequent in patients with solid tumors whereas thrombocytopenia (52%), anemia (36%), neutropenia (36%), fatigue (35%), and nausea (34%) were more frequent in patients with advanced hematologic malignancies. Similar patterns and incidence for serious adverse events (SAEs, grade 3 and 4) were seen for all AEs in patients with solid tumors versus hematologic malignancies. The most SAEs occurring in >5% of patients with solid tumors included fatigue (13%), dyspnea (9%), dehydration (9%), infection (9%), anemia (7%) and neutropenia (7%). The most common SAEs in patients with hematologic malignancies were neutropenic infection (15%) and febrile neutropenia (12%). Fatal (grade 5) events were febrile neutropenia, respiratory failure, neutropenic infection, and disease progression; almost all occurred in patients with hematologic malignancies.

Entinostat has been combined with other systemic treatments [aromatase inhibitors (n=111), erlotinib (n=99), 5-azacytidine (n=319), other agents (13-

cis-retinoic acid, interleukin-2, sorafenib, lapatinib, trastuzumab, nivolumab, ipilimumab; n=211)]. In general, AEs were seen regardless of indication, such as fatigue, nausea, anemia, thrombocytopenia, leukopenia, diarrhea, vomiting, and neutropenia. Again, patients with hematologic malignancies trended to have higher incidences of both AEs and SAEs (62% versus 45%). The incidence of SAEs was also high in patients receiving entinostat in combination with azacytidine (43%). The most frequent SAEs that occurred in entinostat-based studies in 535 patients with solid tumors were decreased absolute lymphocyte count (7%), fatigue (7%), dyspnea (6%), and anemia (5%). Fatal AEs were reported in 15% of the 740 patients treated with entinostat in combination with other agents and were at least twice more frequent in patients with hematologic malignancies compared to those with solid tumors. However, approximately 90% of the fatal AEs were attributed to disease progression.

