4.1 Inclusion Criteria

- 4.1.1 Age \geq 18 years at the time of consent.
- 4.1.2 Subject has provided informed consent and HIPAA prior to initiation of any study-specific activities/procedures.
- 4.1.3 ECOG Performance Status of ≤ 2 .
- 4.1.4 Histologically confirmed metastatic (regional or distant) melanoma of any subtype (cutaneous, mucosal, ocular).
- 4.1.5 AJCC stage unresectable III or stage IV disease that is measurable by RECIST v1.1 criteria.
- 4.1.6 Must agree to undergo one on-treatment tumor biopsy on day 22 (± 2 days) of the study. Subjects for whom fresh samples cannot be safely provided (e.g., inaccessible tumor for biopsy) will not be eligible for study participation.
- 4.1.7 Must have available archival tissue and subjects must have consented to allow collection of archived tumor blocks from previous surgeries confirming or treating unresectable stage III or distant metastatic disease. If more than one archived tumor block is available, only one block is required to be analyzed for the presence of TIL/TALS. Archived tumor tissues must fulfill the following criteria based on two representative H&E-stained tissue sections: (1) the tumor surface area must be at least 1cm^2 (which can be from a combination of metastatic blocks if necessary), (2) no more than 20% of necrosis, (3) the ratio of viable tumor cells to tumor-associated stroma should be at least 60/40, and (4) if TILs are present based on H&E stained

sections, they must be $\leq 1\%$ of the total number of cells in the specimen; the amount of tissue should be ≥ 1 cm².

[name], study pathologist, must sign off on the eligibility of archived tumor blocks before study enrollment. If archival tissue is unavailable or insufficient, fresh biopsy should be performed to confirm unresectable stage III or distant metastatic disease.

4.1.8 Previous treatment with immune checkpoint inhibitors and chemotherapies is allowed on condition that the last treatment is at least 28 days prior to first dose of entinostat. Previous treatment with targeted therapies (e.g. MAPK inhibitors) is allowed on condition that the last treatment was administered at least 15 days prior to first dose of entinostat).

4.1.9 Demonstrate adequate organ function as defined in the table below; all screening labs to be obtained within 21 days prior to entinostat treatment.

System	Laboratory Value
Hematological*	

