Hemoglobin (Hgb)	≥ 9 g/dL or ≥ 5.6 mmol/L without transfusion or erythropoietin dependency (within 7 days of assessment of Hgb)
Absolute Neutrophil Count (ANC)	$\geq 1,500/\text{mm}^3$
Platelets	$\geq 100,000/\text{mm}^3$
Renal*	
Creatinine	≤ 1.5 x upper limits of normal (ULN) OR
Measured or calculated ¹ creatinine clearance (CrCl) (glomerular filtration rate [GFR] can also be used in place of creatinine of CrCl)	≥ 60 mL/min using the Cockcroft-Gault formula for subjects with creatinine levels > 1.5 x institutional ULN
Hepatic*	
Bilirubin	≤ 1.5 xULN OR Direct bilirubin \leq ULN for patients with total bilirubin levels >1.5 xULN
Aspartate aminotransferase (AST)	≤ 2.5 xULN OR < 5 xULN for subjects with liver metastases
Alanine aminotransferase (ALT)	≤ 2.5 xULN OR < 5 xULN for subjects with liver metastases
Albumin	≥ 2.5 mg/dL
Coagulation*	

System	Laboratory Value
International Normalized Ratio (INR) or Prothrombin Time (PT)	≤1.5xULN, unless subject is receiving anticoagulant therapy as long as PT or PTT is within therapeutic range of intended use of anticoagulants
Activated Partial Thromboplastin Time (aPTT)	≤1.5xULN, unless subject is receiving anticoagulant therapy, as long as PT or PTT is within therapeutic range of intended use of anticoagulants

*Note: Hematology and other lab parameters that are ≤ grade 2 BUT still meet criteria for study entry are allowed. Furthermore, changes in laboratory parameters during the study should not be considered AEs unless they meet criteria for dose modification(s) of study medication outlined by the protocol in Section 5.3.1 and/or worsen from baseline during therapy.

4.1.10 A female of childbearing potential must have a negative serum pregnancy test during screening and a negative urine pregnancy test within 3 days prior to receiving the first dose of study drug. If the screening serum test is done within 3 days prior to receiving the first dose of study drug, a urine test is not required. A female of childbearing potential must agree to use effective contraception during the study and for 120 days after the last dose of study drug. A female of non-childbearing potential defined as (by other than medical reasons):

- ≥45 years of age and has not had menses for >2 years,
- Amenorrheic for <2 years without a hysterectomy and oophorectomy and a follicle-stimulating hormone value in the postmenopausal range upon pre-study (screening) evaluation,

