4.2 Exclusion Criteria

All subjects meeting any of the exclusion criteria at baseline will be excluded from study.

- 4.2.1 Is receiving systemic steroid therapy or any other form of immunosuppressive therapy for autoimmune side effects related to previous use of immunotherapies for melanoma. Exceptions include episodic (up to 7 days) use of systemic steroids for common conditions while on study treatment (e.g. COPD exacerbation, poison ivy), use of corticosteroids as replacement doses for adrenal or pituitary insufficiency.
- 4.2.2 Has a known history of tuberculosis (Bacillus Tuberculosis) or human immunodeficiency virus (HIV 1/2 antibodies).
- 4.2.3 Hypersensitivity to pembrolizumab or any of its excipients. Allergy to benzamide or inactive components of entinostat.
- 4.2.4 Has known history of biopsy-proven (non-infectious) pneumonitis that required systemic steroids, or any evidence of current pneumonitis.
- 4.2.5 Conditions that would preclude adequate absorption of oral medications (malabsorption, significant nausea and vomiting, resection of >100 -cm of proximal small bowel, resection of >200 -cm of distant small bowel).
- 4.2.6 Has a history or current evidence of any condition, therapy, or laboratory abnormality that might confound the results of the trial, interfere with the subject's participation for the full duration of the trial, or is not in the best interest of the subject to participate, in the opinion of the treating investigator, including but not limited to:
- i.** Myocardial infarction or arterial thromboembolic events within 6 months prior to screening or severe or unstable angina, New York Heart Association (NYHA) Class III or IV disease, or a QTc interval > 470 msec,
 - ii.** Active infection requiring systemic antibiotic therapy by the first day of entinostat treatment,
 - iii.** Known psychiatric or substance abuse disorders that would interfere with cooperation with the requirements of the trial.

- 4.2.7 If female, is pregnant or breastfeeding, or, if male, expecting to conceive or father children within the projected duration of the trial, starting with the pre-screening or screening visit through 120 days after the last dose of trial treatment.

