6.1.7 AEs Associated with Investigational Drug

As of July 1, 2016, entinostat has been given to >1,055 cancer patients in 31 clinical research studies in the mono-therapy setting and combination setting with another agent(s).

The following side effects occurred in more than 20% of patients with cancer, receiving entinostat alone. These events may or may not be related to entinostat.

- Fatigue (tiredness),
- Nausea,
- Thrombocytopenia,
- Anemia,
- Vomiting,
- Neutropenia,
- Diarrhea,
- Leukopenia,
- Feeling not hungry (decreased appetite),
- Hypophosphatemia,
- Hyponatremia,
- Hypoalbuminemia,
- Headache.

The following side effects were seen in $\geq 10\%$ to 20% of patients, with cancer, treated with entinostat alone. These events may or may not be related to entinostat.

- Shortness of breath or difficulty breathing,
- Constipation,
- Hyperglycemia,
- Hypocalcemia,
- Hypokalemia,
- Swelling in the legs, feet and/or ankles,
- Increase in serum alkaline phosphatase,
- Leukopenia,
- Abdominal pain,
- Fever,
- Cough,
- Muscle pain,
- Salty, metallic taste,
- Indigestion,
- Dehydration.

The following SAE occurred in $\geq 5\%$ of patients with cancer, receiving entinostat alone. These events may or may not be related to entinostat.

- Fatigue,
- Shortness of breath or difficulty breathing,
- Decreased appetite,
- Neutropenia,
- Dehydration,
- Anemia,
- Fever,
- Nausea,
- Abdominal pain,
- Diarrhea,
- Infection,
- Thrombocytopenia.

Overall, the side effects of entinostat when given in combination with other anti-cancer agents were similar to that seen when entinostat was given alone.

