6.4.2 Blood Chemistry Profile

Blood will be obtained and sent to the clinical site chemistry lab for determination of the following: sodium (Na) potassium (K), chloride (Cl), creatinine, blood urea nitrogen (BUN), aspartate aminotransferase (AST), alanine aminotransferase (ALT), total bilirubin, alkaline phosphatase, glucose, total protein, albumin, calcium, magnesium, phosphorus, lactate dehydrogenase (LDH), amylase, and lipase.

All listed serum chemistries will be performed during screening, D1 of each treatment cycle, and at the end of treatment as outlined in the Time and Events table.

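### The albumin entry criterion in 4.1.9 is written in mg/dL, so as printed it excludes no one

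*Combined protocol and SAP*

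**What the plan says.** Section 4.0 requires a subject to meet every eligibility criterion. Criterion 4.1.9 asks the subject to "Demonstrate adequate organ function as defined in the table below". In the hepatic block of that table, the albumin row reads: at least 2.5 mg/dL. No other section gives an albumin limit or a different unit, and neither amendment summary lists a change to this row.

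The only other row in the table expressed as mass per volume is hemoglobin, which is in grams: "≥ 9 g/dL or ≥ 5.6 mmol/L without transfusion or erythropoietin dependency".

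One general exclusion could bear on the same patients. Criterion 4.2.6 applies when a subject "Has a history or current evidence of any condition, therapy, or laboratory abnormality that might confound the results of the trial", interferes with participation, or makes participation contrary to the subject's interest, in the treating investigator's opinion. It sets no albumin number.

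On the drug itself, Section 1.4.6.2.2 sets solid tumours against blood cancers and says of single-agent entinostat that "hypoalbuminemia (59%), fatigue (58%), nausea (57%), hypophosphatemia (45%), anemia (42%), and thrombocytopenia (41%) were more frequent in patients with solid tumors". It introduces the frequent events as "The most frequent adverse effects (AE), predominantly grade 1-2". Section 6.1.7 names hypoalbuminemia in the list headed "The following side effects occurred in more than 20% of patients with cancer, receiving entinostat alone", and adds that these events may or may not be related to the drug. Under Section 6.4.2 albumin is part of the chemistry panel ("alkaline phosphatase, glucose, total protein, albumin, calcium, magnesium, phosphorus"), taken at screening, on day 1 of each cycle and at the end of treatment.

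**The concern.** An eligibility threshold works only if some patients can fail it. A floor of 2.5 mg/dL for a serum protein measured in grams per dL cannot be failed, so a mandatory safety criterion has no effect as printed.

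Three things follow. First, a patient with very low albumin meets the written criterion. Second, a site that silently reads the row as g/dL applies a rule that the protocol does not contain: a patient turned away on that basis was eligible on paper, and one admitted with low albumin is not a recordable eligibility deviation. Section 10.5.2 allows no single-subject exceptions to eligibility, so the written threshold is the one against which compliance is judged. Third, the row concerns a laboratory value that the protocol's own safety summary reports as often abnormal on entinostat. The note under the table does not help, because it admits abnormal values only where they still meet the entry criteria and so refers back to the same row.

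**Working it through.** **Inputs**
- Albumin floor: 2.5 mg/dL (4.1.9, hepatic block).
- Hemoglobin floor: 9 g/dL (4.1.9, hematological block).
- Hypoalbuminemia 59%, fatigue 58%, nausea 57% (1.4.6.2.2).
- Single-agent solid-tumour base: "4 studies in patients with solid tumors (n=128" (1.4.6.2). Using this as the denominator of the 59% is an assumption; the documents do not tie the two together.
- Patient albumin: no range is given. A deliberately wide range of 0.5 to 5 g/dL is assumed.

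**Step 1: convert the floor.** 2.5 mg/dL ÷ 1000 mg/g = 0.0025 g/dL.

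**Step 2: compare patients with the floor.** Multiple = albumin in mg/dL ÷ 2.5.

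| Assumed albumin | In mg/dL | Multiple of the written floor |
|---|---|---|
| 0.5 g/dL | 500 | 200 |
| 1 g/dL | 1000 | 400 |
| 2 g/dL | 2000 | 800 |
| 5 g/dL | 5000 | 2000 |

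Even the lowest assumed value clears the floor 200-fold, so the conclusion does not depend on where in the range patients fall.

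**Step 3: size of the apparent unit error.** If the same number was meant in g/dL, 2.5 g/dL ÷ 0.0025 g/dL = 1000. This is a comparison only, because the documents do not state the intended unit.

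**Step 4: how much weight the 59% can bear.** On a base of 128, 0.59 × 128 ≈ 76 patients (exact 95% CI 50% to 68%) and 0.58 × 128 ≈ 74 patients (49% to 66%). Hypoalbuminemia leads fatigue by one percentage point, about 1 to 2 patients. It is common, but its place at the head of the list carries no weight.

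**Step 5: effect on the design.** The decision rule in Section 9.2 is at least 3 conversions in 10, with P(X ≥ 3) = 1 − Σ C(10,k) p^k (1−p)^(10−k) for k = 0 to 2.
- p = 0.08: 1 − (0.4344 + 0.3777 + 0.1478) = 0.040. The plan states 0.04.
- p = 0.40: 1 − (0.0060 + 0.0403 + 0.1209) = 0.833. The plan states 83%.

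Both figures reproduce, and albumin does not enter either of them.

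**The case against.** The strongest reply is that this is a one-word slip. Any clinician will read the row as g/dL, eligibility is confirmed with the study coordinator before registration (10.3), and an investigator worried about very low albumin can use 4.2.6. Albumin is also monitored every cycle, and no efficacy analysis depends on the row. Much of this stands. The slip has no statistical consequence, and 4.2.6 is a real but partial backstop. What does not stand is that informal reading repairs the criterion: 4.2.6 depends on individual judgement and has no number, and confirming eligibility means confirming it against the printed table.

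A reader might also go further than the documents allow, in three ways.
- *That patients with low albumin at entry would be harmed by a drug that lowers it further.* The documents give no baseline albumin and no outcome by baseline albumin. The frequent events are described as mainly grade 1-2, hypoalbuminemia is not among the grade 3-4 or serious events listed for single-agent use in 1.4.6.2.2 or 6.1.7, and 6.1.7 leaves causality open.
- *That 59% of the 14 planned enrolments (0.59 × 14 = 8.3) measures the problem.* That product estimates events on treatment, which would be the same with a corrected unit. It does not count patients wrongly admitted. The rate also pools single-agent doses and schedules, and the 14 includes an allowance for screen failures.
- *That g/dL was certainly meant.* It is the natural reading, given the hemoglobin row, but no section says so.

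**Conclusion.** The point holds for the albumin row in 4.1.9. As printed, the floor is 0.0025 g/dL and no patient with albumin between 0.5 and 5 g/dL, an assumed range, can fail it; the margin is 200-fold to 2000-fold. If g/dL was intended, the written floor is 1000-fold too low, but that intent is inferred. The conclusion concerns this row and not the eligibility section as a whole, since 4.2.6 remains available without a numeric limit. The reported 59% shows that albumin is relevant to entinostat; it does not size the defect. How many enrolled patients are affected cannot be estimated from the documents. The primary endpoint, its type I error of 0.04 and its power of 83% are untouched. The matter deserves correction because a binding entry threshold has no effect as written.

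**What to change.** The sponsor should confirm the albumin floor and unit that were intended and correct the row in 4.1.9 at the next amendment, in the unit the laboratory reports. Screening albumin already on file for enrolled patients should then be checked against the confirmed criterion, and any patient below it documented under the trial's deviation procedures. This review proposes no value. The cost is one corrected table entry and a look-up of one screening result for each of a small number of patients; no new data collection and no change to the analysis are needed.
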